#### **Exploratory**:

- 1) To evaluate change in HbA1c from baseline to Visit 7
- 2) To evaluate change in HCP views on a connected diabetes management platform
- 3) To evaluate change in participant views on a connected diabetes management platform
- 4) To carry out analysis for calculation of MBDs
- 5) To determine participant interaction with the mobile app and its correlation with MBD change between Study Period 1 versus Study Period 2
- 6) To determine participant CGM wear time and correlation with MBD change between Study Period 1 versus Study Period 2
- 7) To evaluate participant's fear of hypoglycaemia and its correlation with MBD
- 8) To evaluate day and night time CGM profiles during the two periods.

#### **Exploratory:**

- 1) Summary statistics of actual and change in HbA1c between baseline and Visit 7
- 2) Outcome of IORW HCP questionnaires
- 3) Outcome of IORW participant questionnaires
- 4) CGM curves integrated with data received from the Tempo Pen/Smart Button
- 5) Glooko Mobile App data (e.g., number of connections to the app, number of uploads from CGM, number of CCL data uploads, % of CGM data available, number of insulin data available) and comparison of Study Period 1 and Study Period 2 app use
- 6) Summary of CGM wear time data and correlation with MBD data and differences between Study Period 1 versus Study Period 2
- 7) HFS-SF questionnaire score between Visit 1 and Visit 7 and MBD data.
- 8) Summarize nighttime (00:00 AM to 06:00 AM) and daytime CGM profiles during the masked/ unmasked periods.

Abbreviations: B = breakfast; CGM = continuous glucose monitoring; D = dinner; HbA1c = glycated haemoglobin; HCP = healthcare professional; IORW = Study F3Z-MC-IORW; L = lunch; MBD = missed bolus dose; MDSW = medical device software; TAR = time above range; TBR = time below range; TIR = time-in-range.

## 4. Study Design

## 4.1. Overall Design

Study IORW is a multicentre, open-label, controlled, single-arm, pragmatic outpatient study in participants with T1D or T2D that comprises 2 study periods, including:

- a 6-week run-in period (Study Period 1) when insulin timing and dosage data

  CCI is masked to the participant using Glooko RMA and is unmasked to the HCP using Glooko HCP platform, and
- a 12-week intervention period (Study Period 2) when insulin timing and dosage data

  CCl is unmasked to the participant using Glooko RMA and the HCP using Glooko HCP platform.

Study IORW will be carried out in France and will include 9 clinical study sites. The study is expected to last approximately 16 months, with each participant duration of approximately 18 weeks. Approximately 50 participants will be enrolled in the study. Best efforts will be made to enrol a participant ratio of 4:1 for participants with T1D to participants with T2D.

## 4.1.1. Study Period 1 (Run-in) – Weeks 1 to 6 (Baseline)

Following screening, the participants who meet study criteria will:

- receive Sponsor-provided Humalog Tempo Pen and Tempo Smart Button, Dexcom G6 CGM, study-specific Android smartphone, and
- be instructed on how to use the study platform and will receive guidance from the study team on the use of the real time CGM data on the receiver to help them manage diabetes and insulin dosing. They will be trained on how to upload their CGM data on the Glooko RMA.

During that Study Period, mealtime insulin timing and dosage data will not be visible (masked) to the participant using Glooko RMA. Mealtime insulin details will be visible (unmasked) to the HCP using HCP platform. They will also be allowed to track the basal insulin time and dosing and other data (e.g., meals, exercise) manually in the RMA. Baseline (Visit 1 and Visit 3) study questionnaires will also be completed (Table 1.1).

Participants will be asked to follow their pre-study insulin regimen (as prescribed by the investigators), lifestyle and behaviour. The study participant and HCP will not communicate, outside of the scheduled visit and activities described in Table 1.1, except in cases of acute complication, AE and DD reporting, or need for technical support.

Following Study Period 1 (during Visit 3), mealtime insulin timing and dosage data

will be unmasked to the study
participant by HCP. The study participant and HCP will then review and discuss together the
data collected during Study Period 1, including the potential reasons for suboptimal glucose
control. The HCP will be able to propose any educational activities to be taken during Study

Period 2 that would result from the review of the Glooko report, including insulin dose adjustments and other advices deemed appropriate (e.g., missing bolus doses, late injection timing, carb counting).

### 4.1.2. Study Period 2 (Intervention) – Weeks 7 to 18

Following Study Period 1, the participants will enter the 12-week Study Period 2 during which insulin timing and dosage data CCl will be visible (unmasked) to the participant and the HCP in Glooko RMA and HCP platform.

Throughout the entire Study Period 2, data from Humalog Tempo Pen/Smart Button will be transferred to the Glooko RMA. Participants should continue to periodically upload Dexcom G6 CGM during Study Period 2.

Healthcare professionals can monitor participant adherence through the HCP Portal. The participant list displays the date of last sync for each to determine the last Tempo Pen/Tempo Smart Button connection. If necessary, the study site will follow-up with participants to ensure adequate duration of CGM wear and timely Tempo Pen/ Smart Button study data transfer to Glooko RMA. It is recommended that the site does not interact with the participant with respect to their Glooko RMA data during the masked Study Period 1 unless required for participant safety.

See Figure 1.1 for an overview of the study design and Section 6 for more information about the study interventions.

## 4.1.3. Safety Follow-up

Following completion of Study Period 2, study participants will complete their safety follow-up period (Table 1.1).

#### 4.2. Visit Overview

For a quick reference to activities required at each visit, please refer to the SoA (Table 1.1).

#### 4.2.1. Administration of HCP Questionnaires

The **IORW Initial HCP Questionnaire** will be completed by the physician and study coordinator/ nurse prior to FPV at the site.

The **IORW** End-of-study HCP Questionnaire will be completed by the physician and study coordinator/nurse after all participants at the site complete Visit 8 (V8).

## 4.2.2. Visit 1 – Participant Screening and Enrolment

Study participants must give written consent (signed and dated) using the ICF approved by the Sponsor (or its designee) and the governing EC.

This consent is required before any screening assessments are performed and before being allowed to participate in the study.

After an ICF is obtained, participants will commence to study screening.

#### 4.2.2.1. Screening

Study Investigator(s), or qualified designees, will review the participant's medical records and/or history and perform assessments to determine if the participant meets all inclusion and no exclusion criteria to qualify for participation in the study (see Section 5). This includes:

- point-of-care HbA1c measurement, and
- point-of-care urine pregnancy test in women of childbearing age.

Individuals who do not meet the criteria for participation in this study must be screen failed at Visit 1 and may be rescreened (see Section 5.4).

#### 4.2.2.2. Enrolment

If the participant meets all inclusion criteria and no exclusion criteria, they will be enrolled into the study. Study Investigator(s), or qualified designees, will review the participant's medical records and/or history and perform the required study assessments. This includes:

- medical history (including duration of disease)
- current medications
- demographics (excluding ethnicity information)
- physical examination
- vital signs (blood pressure, heart rate, respiration rate, temperature)
- HbA1c
- height, and
- weight.

The nature of any conditions that are present at the time of the physical examination and any preexisting conditions will be documented.

For a complete list of all required assessments, please refer to the SoA (Table 1.1).

Participants previously on non-Humalog insulin will be transitioned to Sponsor-provided Humalog Tempo Pen(s) at doses similar to their current regimen and in accordance with product labelling. All participants including those who were not previously using the Dexcom G6 system will be provided with a study CGM.

This study is not designed as a titration study, but insulin doses may be adjusted to avoid hypoglycaemia or unacceptable hyperglycaemia in the opinion of the HCP.

The site will complete the following activities at Visit 1:

- administer the **IORW Participant Visit 1 Questionnaire and HFS-SF questionnaire** before the Tempo Pen/Smart Button and Glooko RMA is demonstrated
- dispense Humalog Tempo Pen(s)
- dispense Tempo Smart Button(s), and
- provide study CGM and study phone to participants.

The site will guide the participants and document Tempo Pen/Smart Button, Dexcom G6 CGM, and Glooko RMA initialisation activities, including review of the Participant Instructions handout with participants, RMA set-up, correct provision of all required participant information in the RMA. The study site will train the participant in the use of study platform components, review the functioning, understanding, and use of the study platform components and answer any questions relating to the use of the Tempo Pen/Smart Button, Dexcom G6 CGM, and Glooko RMA prior to concluding the visit. Participants will receive guidance from the study team on the use of the real time CGM data on the receiver to help them manage their diabetes and insulin dosing.

Participants will be instructed not to use the Glooko RMA "reminder" feature during study period 1.

Site personnel will review hypoglycaemia management and provide appropriate training to participants (see Section 2.4.3.1).

For a complete list of all required activities, please refer to the SoA (Table 1.1).

#### 4.2.3. Visit 2 - Remote Check-in 1

Visit 2 will be conducted approximately 1 week after Visit 1. Site will perform a remote check-in in which they will review the understanding and use of the study components with participants.

During the visit, the site staff will:

- collect DDs
- collect AEs
- review concomitant medications/changes in medications
- review the functioning, understanding, and use of the study platform components, and
- confirm up-to-date participant CGM and Tempo Pen/Smart Button data was uploaded to the RMA

For a complete list of all required activities, please refer to the SoA (Table 1.1).

## 4.2.4. Visit 3 - In-Person Check-in 1

Visit 3 will be conducted approximately 5 weeks after Visit 2.

At Visit 3, the participant will be required to visit the study site with his/her:

- mobile device with RMA
- CGM
- Dexcom receiver
- Tempo Pen(s) currently in use, and
- Tempo Smart Button.

Unused Tempo Pen(s) may remain at the participant's residence so long as he/she checks how much is remaining to aid in resupply calculations.

During the visit, the site staff will:

- collect DDs
- collect AEs
- review concomitant medications/changes in medications
- review study supplies and dispense, as needed
- review the functioning, understanding, and use of the study platform components
- confirm up-to-date participant CGM data was uploaded to the RMA
- administer IORW Participant V3 Questionnaire
- administer HFS-SF Questionnaire, and
- weigh the participant.

For a complete list of all required activities, please refer to the SoA (Table 1.1).

In addition, following completion of the IORW Participant Visit 3 Questionnaire and HFS-SF Questionnaire, the site staff will unmask the CC data, review the participants' dosing patterns, and discuss information from the HCP Portal with the participant about his/her dosing habits and glucose control collected during Study Period 1.

#### To accomplish this:

- HCPs will be able to display Study Period 1 data on the HCP Portal which will contain previously participant-masked information about insulin dosing and glycaemic status
- the investigator or designee will review Study Period 1 data
- the investigator or designee will share and discuss the data collected during Study Period 1 with the study participant
- dose adjustments and other advices provided by the HCP will be recorded, and
- any educational activities that would result from the review of the report would be documented by the HCP.

#### 4.2.5. Visit 4 - Remote Check-in 2

Visit 4 will occur approximately 1 week after Visit 3. At Visit 4, site staff will perform a remote check-in during which they will review the understanding and use of the study components with participants.

During the visit, the site staff will:

- collect DDs
- collect AEs
- confirm up-to-date participant CGM and Tempo Pen/Smart Button data was uploaded to the RMA
- review concomitant medications/changes in medications, and
- review the functioning, understanding, and use of the study platform components.

For a complete list of all required activities, please refer to the SoA (Table 1.1).

#### 4.2.6. Visit 5 and 6 – Remote Check-in 3 & 4

Visit 5 will occur approximately 3 weeks after Visit 4.

Visit 6 will occur approximately 4 weeks after Visit 5.

Site staff will perform a remote check-in with the participant during which they will:

- collect DDs
- collect AEs
- review concomitant medications/changes in medications
- review the functioning, understanding, and use of the study platform components (if deemed necessary based on previous visits)
- confirm up-to-date participant CGM and Tempo Pen/Smart Button data was uploaded to the RMA
- share and discuss glucose control and insulin dosing habits (adjust the dose if appropriate) with the participant (from last data review, i.e., approximately 4 weeks)
- document any educational activities that would result from the review of the report by the HCP, and
- review study supplies status.

For a complete list of all required activities, please refer to the SoA (Table 1.1).

#### 4.2.7. Visit 7 – In-Person Check-in 2

Visit 7 will occur approximately 4 weeks after Visit 6.

At Visit 7, the participant will be required to visit the study site and bring his/her:

- mobile device with RMA
- CGM
- Dexcom receiver
- Tempo Pen(s) currently in use
- unused Humalog Tempo Pen(s), and
- Tempo Smart Button.

Participants will return all appropriate Sponsor-provided study materials as per Sponsor instructions.

During the visit, the site staff will:

- collect DDs
- collect AEs
- review concomitant medications/changes in medications

- confirm up-to-date participant CGM and Tempo Smart Button data was uploaded to the RMA and
- review and discuss glucose control and insulin dosing habits (since last visit, i.e., approximately 4 weeks) with the participant, using the HCP Portal information.

The site will also perform the following assessments:

- weight, and
- point-of-care HbA1c measurement.

In addition, following review of the summary on Glooko HCP platform and discussion with the participant, the site staff will administer the **IORW Participant Visit 7 Questionnaire and HFS-SF Questionnaire** to the participant.

After Visit 7 is complete, participants will transition to a non-study insulin regimen and a non-study CGM device (if applicable).

For a complete list of all required activities, please refer to the SoA (Table 1.1).

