## 1.3. Schedule of Activities

Table 1.1 summarises the Schedule of Activities (SoA) for the study.

Table 1.1. Schedule of Activities for Study F3Z-MC-IORW

	Study Pe	eriod 1 (Masl	ked)	Stu	Study Period 2 (Unmasked)				UNS	ET
Visit Number	V1	V2	V3	V4	V5	V6	V7	V8 or ET(Exit)		
Visit Type	On-site	Remote	On-site	Remote	Remote	Remote	On-site	Remote		
Time from previous visit (weeks or days)	N/A	1 W	5 W	1 W	3 W	4 W	4 W	3D	N/A	N/A
Visit window (days)	N/A	+/-3	+7	+/-3	+/-3	+/-3	+7	+/-1	N/A	N/A
Study Logistics	-	 		<del>-</del>	-				-	
Informed Consent signed	X									
Eligibility Criteria Reviewed	X									
Enrolment	X									
Install and set-up Glooko RMA	X									
Pair the Tempo Smart Button	X									
Study CGM device user training provided	X									
Study phone user training provided	X									
Complete Participant Training	X									
Participant brings mobile device with RMA and Tempo Pen with Tempo Smart Button			X				X			X
Confirm Tempo Smart Button transfer onto Glooko RMA			$X^1$		$X^1$	X 	$X^1$		X 	X 
Review the functioning, understanding, and use of the study platform components	X	X	X	X	$X^2$	$X^2$			$X^2$	

	Study Per	Period 1 (Masked)			ıdy Period	2 (Unmask	ed)	Follow-up	UNS	ET
Visit Number	V1	V2	V3	V4	V5	V6	V7	V8 or ET(Exit)		
Visit Type	On-site	Remote	On-site	Remote	Remote	Remote	On-site	Remote		
Time from previous visit (weeks or days)	N/A	1 W	5 W	1 W	3 W	4 W	4 W	3D	N/A	N/A
Visit window (days)	N/A	+/-3	+7	+/-3	+/-3	+/-3	+7	+/-1	N/A	N/A
Unmask Tempo Pen data in Glooko RMA			X							
Clinical Assessment and Diab	etes Management									
Medical History (including pre-existing conditions)	X									
Demographic information	X									
Height and Weight	X		$X^3$				$X^3$			$X^3$
Physical Examination	X									
Urine PoC Pregnancy Test (WOCBP only)	X									
HbA1c PoC Test	X						X			X
Vital Signs	X									
Hypoglycaemia management and training	X		$X^4$		$X^4$	$X^4$			X 	QR
Review concomitant medications	X	X	X	X	X	X	X	X	X	X
Review Adverse Events	X	X	X	X	X	X	X	X	X	X
Review Device Deficiencies (DD)	X	X	X	X	X	X	X	X	X	X
Review of glucose values and insulin regimen with participant (adjust if appropriate)	X		X 		X 	$X^5$	X 			X 
Document any educational activities			$X^6$		$X^6$	$X^6$	$X^6$			$X^6$
Study Material Management										
Dispense Tempo Smart Button	X								X 	
Dispense Humalog Tempo Pens	X		X						X 	

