### 4.3. Early Discontinuation Visits

Participants discontinuing from the study prematurely, for any reason, should return to the study site.

The participant will be required to bring his/her:

- mobile device with RMA
- CGM
- Dexcom receiver
- Tempo Pen(s) currently in use
- unused Tempo Pen(s), and
- Tempo Smart Button.

Participants will return all appropriate Sponsor-provided study materials as per Sponsor instructions.

During the visit, the site personnel will:

- collect DDs
- collect AEs
- review concomitant medications/changes in medications
- confirm up-to-date participant CGM and Tempo Smart Button data was uploaded to the RMA, and
- review and discuss glucose control and insulin dosing habits (adjust the dose if appropriate) with the participant, using the Glooko HCP Portal information.

The site will also perform the following assessments:

- weight, and
- point-of-care HbA1c measurement.

In addition, following review of Glooko summary report and discussion with the participant, the site staff will administer to the participant:

- the IORW Participant **Visit 3** Questionnaire and HFS-SF Questionnaire if the Early Termination visit takes place before Visit 3,
- the IORW participant **Visit 7** Questionnaire and HFS-SF Questionnaire if if the Early Termination visit takes place after Visit 3.

For a complete list of all required activities, please refer to the SoA (Table 1.1).

Site personnel should document details regarding the reason for discontinuation, if possible (see Section 7). Study participants will transition back to their non-study insulin (if applicable) and their non-study CGM devices (if applicable).

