4.4.1.1.10. Participant and Healthcare Professional Questionnaires

Each question from participant and HCP questionnaires will be summarized in a table using frequency and percentages. Participant questionnaire summaries at Visits 1 (baseline) and Visit 3 (end of Study Period 1) from Study Period 1 will be compared to summaries at Visit 7 from Study Period 2 using shift tables. HCP questionnaire summaries will compare initial to end of study. No formal statistical testing is planned.

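### Participant questionnaire and HFS-SF precede the data discussion at Visit 3 but follow it at Visit 7 and at early termination, so comparisons with Visit 7 carry any same-day effect of that discussion

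*Protocol*

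**What the plan says.** The protocol fixes the order of self-report and clinician contact visit by visit.

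- **Visit 1 (Protocol 4.2.2.2).** The Visit 1 questionnaire and HFS-SF are given "before the Tempo Pen/Smart Button and Glooko RMA is demonstrated". The Schedule of Activities (Protocol 1.3) also marks this row at Visit 1: "Review of glucose values and insulin regimen with participant (adjust if appropriate"). It does not say whether that review comes before or after the instruments.
- **Visit 3 (Protocol 4.2.4).** Unmasking and review take place only "following completion of the IORW Participant Visit 3 Questionnaire and HFS-SF Questionnaire". Staff then "discuss information from the HCP Portal with the participant about his/her dosing habits and glucose control collected during Study Period 1".
- **Visit 7 (Protocol 4.2.7).** The Visit 7 questionnaire and HFS-SF are administered "following review of the summary on Glooko HCP platform and discussion with the" participant.
- **Early termination (Protocol 4.3).** The instruments come "following review of Glooko summary report and discussion with the participant". This covers both the Visit 3 form, for those leaving before Visit 3, and the Visit 7 form, for those leaving later.

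Protocol 6.3 presents the questionnaires at Visits 1, 3 and 7 as the source of baseline and endpoint data. Under SAP 4.4.1.1.10, participant summaries from Visits 1 and 3 "will be compared to summaries at Visit 7 from Study Period 2 using shift tables", with no formal test. SAP 4.5.7 summarises HFS-SF at Visits 1 and 7, takes the change, and relates the scores to missed bolus doses (MBD) by Spearman correlation. Neither document gives a reason for the differing order.

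**The concern.** A before-and-after comparison of self-reported scores is easiest to read when the scores are collected in the same circumstances each time. Here the participant answers at Visit 3 without having just talked through the dosing and glucose record with the clinician, and answers at Visit 7 directly after doing so. Such a conversation could reassure or alarm. It could also draw more agreeable answers about satisfaction from someone who knows what is being studied.

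There is no comparator arm in which the same order effect would appear and cancel. What is at stake is whether a movement between Visit 3 and Visit 7 describes 12 weeks with the unmasked platform, or partly describes that day's conversation.

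**Working it through.** The plan states no figure for this point, so the check is a comparison of the texts followed by a short piece of algebra.

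**1. Order at each visit**

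| Visit | Instruments relative to the discussion of platform data | Used in |
|---|---|---|
| 1 | Before the platform is demonstrated; order relative to the glucose and regimen review not stated | Shift tables; HFS-SF change |
| 3 | Before | Shift tables (HFS-SF at Visit 3 is not named in SAP 4.5.7) |
| 7 | After | Shift tables; HFS-SF change |
| Early termination | After | Not assigned to an analysis in SAP 4.4.1.1.10 or 4.5.7 |

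The exact reversal is Visit 3 against Visit 7.

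**2. Effect on the Visit 3 to Visit 7 comparison.** Let θ be the mean change that would be seen if participants answered on arrival at Visit 7, and b the mean immediate effect of the Visit 7 discussion. Then

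mean(Visit 7 − Visit 3) = θ + b.

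The term b enters one for one, and sample size does not appear, so more participants would not remove it. It cannot be estimated from the trial, because everyone at Visit 7 is assessed in the same order. In a shift table it would appear as moves between response categories.

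**3. Effect on the Visit 1 to Visit 7 HFS-SF change.** Let θ₁ be the corresponding change from Visit 1, and a the immediate effect of the Visit 1 glucose and regimen review if it came before the instruments (a = 0 if it came after). Then

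mean(Visit 7 − Visit 1) = θ₁ + b − a.

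The documents do not settle a. The HFS-SF change may therefore carry all of b, or b partly or wholly offset.

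**4. Effect on the Spearman correlation with MBD.** Spearman uses ranks. Adding the same b to every Visit 7 score leaves the ranks of those scores unchanged, and likewise the ranks of the change scores. Taken within one visit or on change scores, the correlation moves only if the shift differs between participants.

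**5. Early exits before Visit 3.** Protocol 4.3 bases the exit discussion on HCP Portal information about glucose control and dosing habits. Someone leaving before Visit 3 therefore completes the Visit 3 form after such a discussion, whereas someone attending Visit 3 completes it before. The same form is collected in two different circumstances.

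**6. Reach.** The scores serve secondary objective 10 (preference, satisfaction, convenience, ease of use), exploratory objective 3 (participant views) and exploratory objective 7 (fear of hypoglycaemia). MBD is derived from glucose sensor and Smart Button data (SAP 4.3.1.1) and does not depend on when a questionnaire is filled in.

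**The case against.** The strongest reply is that the difference is deliberate. At Visit 3 the instruments come first so that they still describe the masked period. At Visit 7 there is no mask left to protect. Conversations based on platform data are presented as a route to benefit (Protocol 2.4.1), so asking for views after the last one measures the whole intervention. This is a fair reading, and it explains the Visit 3 rule. It does not require the Visit 7 rule. Data discussions have already taken place at Visits 3, 5 and 6, and participants see their own dosing data throughout Study Period 2. Answers given on arrival at Visit 7 would still reflect the 12 weeks and would leave out only that day's conversation.

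Several limits do stand:

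- A reader might infer that Visit 1 has the same order as Visit 3, so that the HFS-SF change certainly runs from before a review to after one. The protocol says only that the instruments precede the demonstration of the platform.
- A reader might infer that the correlation with MBD is biased. A uniform shift would not alter it.
- The questionnaire items are not in the documents, so how many Visit 7 items feed the shift tables is unknown.
- The SAP sections concerned do not say where a pre-Visit 3 exit score would be used. Protocol 7.2.2 expects discontinuation to be uncommon, although Protocol 9.4 allows 35% for dropout and missing sensor data, so the number of such scores cannot be judged.
- Courtesy in an open-label, staff-administered setting would not vanish under another order, and an uncontrolled change would still not be attributable to the platform alone.

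**Conclusion.** The point holds for Visit 3 against Visit 7, and for the Visit 3 form given at early termination. Any same-day effect of the Visit 7 discussion enters the Visit 7 scores and hence the Visit 3 to Visit 7 shift tables. It may enter the mean Visit 1 to Visit 7 HFS-SF change. It reaches the Spearman correlation with MBD only if it varies between participants, assuming the correlation is taken within a visit or on change scores.

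The documents give neither the size nor the direction of the effect, and no standardised size should be attached to it. Nor do they support a claim that every baseline score is free of a preceding review while every endpoint score follows one. Visit 1 is open on this, and early leavers complete the Visit 3 form after a discussion.

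The consequence is modest. The primary endpoint is unaffected. The questionnaires are summarised without testing, SAP 4.5.7 plans no test of the mean HFS-SF change, and only one secondary and two exploratory objectives are involved. This is a cheap improvement and does not threaten the trial's main conclusion.

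**What to change.** In Protocol 4.2.7 and 4.3, have HFS-SF, and the questionnaire items that feed the shift tables, completed before the Glooko summary is reviewed and discussed, as at Visit 3. Items asking about the final review itself may stay after it. It would also help to state where the instruments fall relative to the glucose and regimen review at Visit 1.

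The cost is about one sentence in each section and in the site instructions, with the same visit, staff and forms. There are two downsides. Participants already assessed in the present order must be flagged, since their Visit 7 or exit scores were collected differently. The Visit 7 score would also no longer reflect the final discussion.

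If the order cannot be changed, the SAP and clinical study report should state it as a limitation wherever Visit 7 scores are compared with earlier ones.
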